#### 4.3.2 Assessment of Relationship to Study Agent

The relationship of all AEs to DAA will be assessed per the package insert and investigator's brochure for DAA, and clinical judgment of the investigator. The relationship categories that will

be used for this study are related and not related, as defined in the Manual for Expedited Reporting of Adverse Events to DAIDS (Version 2.0, dated January 2010) which is available at <http://rsc.tech-res.com/safetyandpharmacovigilance/>.

### 4.4 Reporting Requirements for this Study

The Serious Adverse Event (SAE) Reporting Category, as defined in Version 2.0 (or latest version) of the DAIDS EAE manual, will be used for this study. The study agents for the purposes of SAE reporting are part of a fixed dose combination tablet: sofosbuvir/daclatasvir or sofosbuvir/velpatasvir.

The SAE reporting period for this study is per the DAIDS EAE manual and continues from enrollment of a trial participant to the end of trial follow-up for that participant. All reportable SAEs occurring during the study reporting period will be reported to the principal investigator in an expedited manner, within three reporting days of site awareness of the events (see definition in Appendix D of the DAIDS EAE Manual).

Reporting requirements for the local IRB will also be followed.

### 4.5 Social Harms Reporting

Although study sites will make every effort to protect participant privacy and confidentiality, it is possible that participants' involvement in the study could become known to others, and that social harms may result. For example, participants could be perceived as being HIV-infected or at high risk for HIV infection and be treated unfairly or have problems being accepted by their families and/or communities. Social harms that are judged by the PI/designee to be serious or unexpected will be reported to the responsible site's IRB at least annually, or according to its individual requirements.

Social harms will be collected and reported on forms during regular visits. In the event that a participant reports social harm, every effort will be made by study staff to provide appropriate care and counseling to the participant, and/or referral to appropriate resources for the safety of the participant. Each site will provide such care and counseling in accordance with standardized guidance in the SOP.

### 4.6 Toxicity Management

The site clinician has the discretion to hold DAA at any time if s/he feels that continued medication use would be harmful to the participant or interfere with treatment deemed clinically necessary according to the judgment of the investigator. Clinical or laboratory abnormalities that require follow up will be documented, and the research associate or clinician will contact the participant to schedule an interim visit for follow-up and/or repeat laboratory testing. All participants reporting an adverse event will be followed clinically until the occurrence resolves (returns to baseline grade, defined as grade at enrollment) or stabilizes or an effective referral to local health care providers is accomplished.

#### 4.6.1 Discontinuation of Study Medication

##### Grades 1 or 2

Continue DAA treatment at the discretion of the site investigator.

##### Grade 3

DAA may be continued at the discretion of the site investigator if a Grade 3 toxicity is considered to be unrelated to the study medication. Study medication will be temporarily withheld if Grade 3 toxicity is considered to be related to the study medication. After a Grade 3 toxicity returns to Grade 1, the participant can be reintroduced to medication after consultation with the site investigator, and other members of the CMC. If a Grade 3 toxicity recurs and is considered to be related to study medication, DAA will be permanently discontinued.

### Grade 4

For all Grade 4 laboratory-identified or clinical toxicities, DAA will be withheld unless it is determined to be not related. If a Grade 4 laboratory toxicity is not confirmed by repeat testing, it should be managed per algorithm for the new toxicity grade. Participants with Grade 4 AEs will be followed until the event resolves to baseline or stabilizes. Study drug may be restarted in the event of the resolution of a Grade 4 AE back to Grade 1, after consultation with the site investigator, and other members of the CMC. If the toxicity recurs to Grade 3 or higher after DAA is restarted and is considered to be related to DAA, the study medication will be permanently discontinued.

### 4.7 Concomitant Medications

With the exception of medications listed as prohibited in the paragraph below, enrolled study participants may use concomitant medications during study participation. All concomitant medications, including prescribed and over-the-counter preparations, vitamins and nutritional supplements, recreational drugs and herbal preparations reported within 45 days prior to confirmation of eligibility for study enrollment and throughout the course of the study will be recorded on the form designated for that purpose. Medications used for the treatment of AEs that occur during study participation will also be recorded on applicable study forms. Participants who begin taking any medication during the trial that is listed as an exclusionary medication at Screening will temporarily discontinue study drug. Study drug may be resumed if no exclusionary medication has been taken in the last 4 weeks.

Should participants report use of any of the following medications, they will be required to discontinue use of study drug: interleukin therapy, medications with significant nephrotoxic potential (including but not limited to amphotericin B, aminoglycosides, cidofovir, foscarnet and systemic chemotherapy), and medications that may inhibit or compete for elimination via active renal tubular secretion (including but not limited to probenecid).

## 5 Human Subjects

### 5.1 Overview

This study involves minimal risk to human subjects since all clients enrolled will be already receiving OAT and national recommendations are for all HCV positive individuals to be diagnosed and treated. Most primary data will come from clinical record-keeping, external clinical data collection procedure and participant surveys, which will be done without unique identifiers. Participants will differ solely in the site where they receive it. We will conduct a stratified cluster randomized study to compare HCV treatment cascade outcomes among OAT clients in 12 regions in Ukraine. We will use ECHO (Extension for Community Healthcare Outcomes) in HCV care to train health care providers to provide integrated care for HCV (SHIM). Of note, HCV treatment and ECHO facilitation are all evidence-based practices. Additionally, we will conduct quantitative and qualitative interviews and focus groups to assess organizational, community and structural factors that promote or impede the successful SHIM integration into OAT clinics. Quantitative and in-depth interviews will be conducted among staff, and administrators, and focus groups will be

conducted with clients. We will also quantitatively survey staff and administrators to assess organizational factors. No personal identifiers will be collected.

### 5.2 Description of the Population Being Studied

In this study (Aims 1 and 3) we will enroll all OAT clients within sites that agree to participation. As part of Aim 2, in addition to the study participants, we will interview and survey clients, clinicians and health center administrators from participating OAT clinics.

### 5.3 Storage of Data

Data from all the sites will be uploaded into a data warehouse system using REDCap. The REDCap database will be password protected and only available to research-affiliated staff at UIPHP. Only de-identified data will be made available to researchers. All information gathered from the study data sources will be stored in password-protected computers with double-password protection for opening specified files. All computers have been encrypted in accordance with stringent security policies. All essential research documentation will be stored in the double-locked research offices at UIPHP. Subject information will be stored with research study number and without any unique identifiers. The data will be stored in the manner noted above for at least three years after completion of the study.

### 5.4 Potential Risks

As in all research studies, there are potential risks. We go to great efforts, however, to ensure that risks are minimized.

Potential Risks Associated with HCV Diagnosis and Treatment Procedures: While HCV diagnosis and treatment is an EBP, risks may occur as part of routine clinical care. Importantly, this research is not studying new medications or diagnostic procedures. The patients will be prescribed only procedures or medications currently registered in Ukraine for diagnosis or treatment of respective clinical conditions. These procedures and medications may have certain side effects. To reduce these risks, even though all clinicians at these sites are trained in managing common complications and side effects, we will review this in great detail during the 2-day training session.

Risks Associated with Data Transfer: During the entirety of this study, patient information will be collected and transferred to UIPHP's research office using STMA encrypted datasets or REDCap data collection system WITHOUT any distinct patient identifiers. The external clinical data collection procedure involves using patients name to obtain data from other healthcare facilities, but the name is not recorded on any paper or electronic forms. There are no risks to the patients associated with this part of the study because all data will be de-identified before transfer to UIPHP. De-identification involves the removal of all identifying information, such as name, address, telephone number, date of birth and social security number. Individual locator information will be stored at the clinical research sites, and UIPHP staff will not have access to these records. Age, however, will remain on the record, as it is useful for our analysis and is not individually identifying information.

Risks Associated with Qualitative Assessments: Some clients, medical personnel and administrators from the OAT sites will participate in qualitative interviews or focus groups. Even though the participants are clients, medical professionals or administrators who will be talking about their patients, providers, or facilities, some of these topics may make some participants feel uncomfortable. Participants will be informed that they may choose not to answer all or any part of a question they are uncomfortable with during the interviews. Prior to interviewing, they will be given an information sheet and will be asked if they would like to participate. They will be given the option to take time and think about it. They may choose to withdraw from the study at any

point and decide not to come in for the interviews. During the interviews, participants may choose not to answer a question or part of a question and are free to give as little or as much information as they feel comfortable. Data from the audio-recorded interviews will be reviewed after they have been completed. No study-related unanticipated problems or adverse events are expected to occur in this part of the study. Hard copies of data collected will be stored in a locked cabinet behind double-locked doors. Electronic records of the interviews will be password-protected.

Risks Associated with Staff Surveys: Medical personnel and administrators from the participating medical centers will complete surveys. In the surveys, they may be asked questions on topics that may make them feel uncomfortable. There are minimal risks expected from completing questionnaires, such as feeling uncomfortable with certain topics. Similar to the protections of the face-to-face interviews above, if anyone feels uncomfortable, they may choose not to answer any part or all of a question. During the initial consent procedures, they will be fully informed about all parts of the questionnaires, and will be asked whether they would like to participate in the study. They may choose to withdraw from the study at any point and decide not to complete the survey but our experience has been nearly 100% acceptance since none of their individual responses will be reported and only aggregate data will be provided. No study-related unanticipated problems or adverse events are expected to occur in this part of the study. All data will be collected using REDCap and maintained on password protected computers.

Risks Associated with Patient Surveys: The surveys will be performed using an online REDCap system, either on a tablet or on a computer. There are minimal risks expected from completing questionnaires, such as feeling uncomfortable with certain topics. The patients will be told that they can refuse to answer any of the survey if they feel uncomfortable and that their responses will be kept anonymous and will in no way affect their receipt of care or treatment at the medical facility. During initial consent procedures, they will be fully informed about all parts of the study, including the questionnaires, that they will not be identified aside from the clinic where they receive their OAT, will be asked to read the informed consent form, and will be asked whether they would like to participate in the study. They may choose to withdraw from the study at any point and decide not to complete the survey. If they choose not to complete the online survey, they will be asked why (e.g., concerned about confidentiality, too busy, etc). No study-related unanticipated problems or adverse events are expected to occur in this part of the study. Electronic copies of the questionnaires will be password-protected. In no way will their responses be relayed to the clinical staff and jeopardize the relationship with their clinical providers.

Risks Associated with Loss of Confidentiality: As with all research, there is a risk that involves potential breaches of confidentiality. We intend to do everything possible to reduce this risk and this is one of the process measures we propose to measure. As part of this study, subjects who are OAT patients, medical practitioners or administrators will be interviewed in private rooms within their facilities. Potential sites for breaches of confidentiality include the recruitment process, the study interviews, or at data management systems. All information is stored in password-protected, encrypted computers with double-password protection for opening specified files. All confidential information (ICFs, study instruments, medical records, audio files, etc.) will be recorded with study participant number only and maintained in locked cabinets within offices at UIPHP and will only be available to be opened by the Data Manager, Study Coordinator, Co-Investigators or the Principal Investigator. Electronic databases will be maintained through password-protected computers and files.

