A systematic training on SHIM for OAT physicians participating in the study will be conducted by the sub-group experts and will cover all parts of the SHIM manual.

Training on research procedures for interviewers and clinical data collectors will occur simultaneously with the intervention training. All research procedures, including participant recruitment (with informed consent), assessment, clinical data collection, etc) will be presented using the Standard Operating Procedures.

Under close supervision of the national experts, we will pilot the manual on a small sample of patients (N=20) at a large OAT site in Lviv. Considering the timeline, the pilot phase will assess HCV care continuum stages up to SVR12. The pilot participants will also undergo all research-related procedures developed for the main phase trial (see the Aim 3 section).

### 3.4 Research methods for Aim 2

3) Using a multi-level implementation science framework, to examine the client, clinician and organizational factors that contribute to SHIM adoption and clinical outcomes.

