### 3.5.1 Design overview

Individual randomization of subjects within each site would likely lead to a high degree of cross-contamination between the study groups because the selected interventions are designed to sustainably change the provider knowledge and practice. Therefore, we have chosen a cluster-randomized trial design, where participating sites will be randomly assigned to one of the three implementation arms. Based on our preliminary studies suggesting region-specific differences in HCV level among OAT patients, we will stratify 12 OAT sites by 4 defined geographic regions (Center, East, South, West) at a 1:1:1:1 ratio. To achieve the desired sample size (see Sample Size section) and retain equal size in each group, we will select and match 3 clinics across the 4 regions. One clinic per triplet will be randomized to one of the three arms: Standard of Care, SHIM and SHIM+ECHO (see Study Conditions), resulting in total 4 clinics per arm. Each clinic will aim to recruit 40 patients. In case of clinic's capacity the availability of DAA medication in region, the clinic's capacity to include in treatment and monitor the course of treatment of a larger number of patients) the number of participants can be increased up to 60). All sites will follow the same patient recruitment and data collection procedures.

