For the secondary outcomes S2b-c, we will collect data using a **paper-based adherence form** administered by clinical personnel during patient visits at treatment initiation, medication pick-up at 4 and 8 weeks, and treatment completion at 12 weeks after initiation. The baseline form will assess self-efficacy and anticipated barriers to treatment adherence for the whole treatment period. The follow-up forms will assess treatment satisfaction, past 30-day and 7-day adherence using visual analog scale [36], side effects, reasons for non-adherence, and reasons for treatment discontinuation (if occurred). At treatment completion, the form will additionally assess the readiness and anticipated barriers to SVR check at 12 weeks after.

For the secondary outcomes S2a and S3a and relevant co-variables, we will collect data using a **patient survey**. The survey will be conducted for the pilot patients and all 3 arms of the main phase at baseline, treatment completion (or 12 weeks after initiation if not completed or 16 weeks after the baseline if not started) and 12 weeks after treatment completion (or 24 weeks after treatment initiation if not completed, or 28 weeks after the baseline if not initiated treatment).

The baseline survey will be administered after confirmation of the diagnosis using HCV RNA test. Patients who will test negative for HCV RNA will be excluded from the following study procedures.

All patient surveys will be collected by an independent interviewer, using study ID via UIPHP REDCap server with clerical checking and patient safeguards described in detail in the human subjects section.

The surveys will include demographics, geospatial assessment, depression (PHQ-9), substance use, alcohol use disorders (AUDIT-C), HIV comorbidity and treatment history, Chronic Liver Disease Questionnaire-Hepatitis C Version (CLDQ-HCV) [37], trust in physician scale [38, 39], HIV risk behaviors, family and social support [40], drug use and mental illness stigma [41], and socio-demographic information.

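### Section 5.4 bars passing patient survey answers to clinical staff with no exception for safety or participant agreement, although the survey carries the PHQ-9 three times and Section 5 gives no step for a concerning score

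*Combined protocol and SAP*

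**What the plan says.** The paragraph on patient surveys in Section 5.4 (Potential Risks) ends with: "In no way will their responses be relayed to the clinical staff and jeopardize the relationship with their clinical providers". Nothing after it qualifies the rule. The same paragraph describes the answers as anonymous and expects no adverse events from this part of the study.

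Section 3.5.6 (Data collection) lists among the survey content "depression (PHQ-9), substance use, alcohol use disorders (AUDIT-C". It also states that "All patient surveys will be collected by an independent interviewer", under a study ID on the REDCap server, and it refers to the human subjects section for patient safeguards. On timing, "The survey will be conducted for the pilot patients and all 3 arms of the main phase at baseline", then at treatment completion and 12 weeks after that. Substitute dates are given for participants who do not finish or do not start treatment.

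On access, Section 5.3 says "The REDCap database will be password protected and only available to research-affiliated staff at UIPHP". Section 5.4 adds: "Individual locator information will be stored at the clinical research sites, and UIPHP staff will not have access to these records".

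**The concern.** A depression questionnaire given repeatedly to patients in opioid agonist treatment (OAT) can be expected to return some high scores. Under the rule as written, such a score may not go to the OAT clinicians, who according to Section 3.1.2 see patients daily or regularly. This holds even if the participant wants them told. The protocol gives research staff nothing to do instead: no cut-off, no referral list and no person to call.

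Some participants may have little clinic contact. Section 3.5.7 keeps people in the study after discharge from OAT, and Section 3.5.6 still surveys those who never start treatment, at 16 and 28 weeks after baseline. For them the survey may be one of the few remaining contacts.

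The bar has a good purpose. The same survey asks about substance use, trust in the physician and stigma, and honest answers need protection. What is at stake is participant safety, not the validity of any trial result.

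**Working it through.** The plan states no figure on this point, so the check sets the sections side by side and then counts exposure.

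**1. Is the PHQ-9 in every survey?** Section 3.5.6 lists it for the surveys in general and names the additional baseline content separately. The survey dates in the text and the schedule table agree on three time points. Section 3.5.5 mentions four interviews, but only for the SF-12, and no fourth date appears anywhere. Three is the supported count.

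**2. Is the safeguard where the protocol says it is?** Sections 5.1 to 5.7 cover consent, storage, private rooms, compensation, the right to skip questions and ethics approval. None gives a PHQ-9 threshold, a referral step or a duty on the interviewer. Section 5.5 has a protection paragraph for qualitative assessments and staff surveys. For patient surveys it says only that the main consent form governs them.

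**3. Does another route cover it?**

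| Route | What it covers | Link to survey answers |
|---|---|---|
| Section 4.2 | Grade 3 or higher clinical adverse events go to a study clinician (role not defined) | None stated |
| Section 4.5 | Care, counselling or referral when a participant reports social harm | None stated |
| Section 4.1 | The monitoring committee reviews safety reports from site coordinators | No text puts survey scores in them |
| Section 3.5.6, chart review | Mental health screening recorded by the clinic | A separate data source |

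None is said to override Section 5.4. A score first noticed centrally would also have to go back through the interviewer or the site, because central staff hold no locator data.

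**4. Exposure count.** Inputs: 480 participants and 12 clinics (Section 3.5); an allowance per clinic under which "the number of participants can be increased up to 60" (Section 3.5.1); three surveys (step 1).

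- Target enrolment: 480 x 3 = 1,440.
- Every clinic at its maximum: 12 x 60 = 720, and 720 x 3 = 2,160.
- With 90% completing each follow-up survey: 480 + 432 + 432 = 1,344, or 720 + 648 + 648 = 2,016. Section 3.5.8 expects more than 90% of survey data at 24 weeks; the same rate at treatment completion is assumed.
- Pilot: Section 3.3 says "we will pilot the manual on a small sample of patients (N=20"), so 20 x 3 = 60. Section 1 reports the pilot as done, so a change would not reach those.

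These are upper counts. Only RNA-confirmed patients are surveyed (Section 3.5.6), whereas Section 3.5.8 counts as enrolled those who screened positive. If the 480 includes patients later found RNA-negative, the number of surveys is lower.

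**5. People, as a scale only.** The documents give neither a prevalence of severe depression nor a cut-off. If 2% to 10% of participants had a result above the chosen threshold (an assumption), that is 480 x 0.02 = 9.6 to 480 x 0.10 = 48 people, or 14.4 to 72 of 720.

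**The case against.** The strongest reply is that the missing step may exist elsewhere. Section 5.5 places survey participation under the consent form, and Section 3.3 places research procedures under SOPs. Neither is in the copy reviewed, and both are natural homes for a limit on confidentiality and a distress procedure. This stands, and it limits the point to the protocol text. It does not remove it: Section 3.5.6 names the human subjects section as the place for these safeguards, and an SOP exception would conflict with the unqualified sentence in Section 5.4.

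Second, the bar is narrower than it may look. It covers relay to clinical staff. It does not stop the interviewer giving the participant referral information or contacting the principal investigator or the clinical consultant on the monitoring committee. This stands. The sentence might even be read as forbidding only disclosure that damages the clinical relationship. The plain reading is a full bar, however, and an interviewer should not have to choose between readings.

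Third, it is tempting to infer that the interviewer is the first to learn of a high score and then has no way to act. The documents do not establish this. Section 3.5.6 says an interviewer collects the surveys, while Section 5.4 describes online completion on a tablet or computer. Neither says who sees or scores the answers, or when. If patients complete the form themselves, nobody may look at the score that day. This changes what the remedy needs.

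Fourth, the TB referral in Section 3.5.3 is not a fair precedent: clinical staff carry it out, as part of eligibility screening. The social-harm step in Section 4.5 is the closer comparison, and it also leaves operational detail to an SOP.

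**Conclusion.** The point holds in a limited form. Section 5.4 states an unqualified bar, the survey it governs carries the PHQ-9 at three time points, and the section named as holding the safeguards contains none for a concerning depression result. Following the text as written is worse for patient safety than a rule with a narrow exception, so this is more than missing detail.

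A reader might infer more, and the documents do not support it:

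- **Suppressed adverse events.** Sections 4.2 to 4.4 remain in force. How they interact with Section 5.4 is unclear, not contradictory.
- **Participants denied all help.** Clinic charts carry separate mental health screening, and the documents do not show how many high scorers the clinic would already know about.
- **1,440 people or events at risk.** This is a maximum number of questionnaires at target enrolment.
- **A known self-harm answer withheld.** The protocol names the PHQ-9 but describes no item, score or cut-off.

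The conclusion assumes that the survey is given at the three scheduled times and that the consent form and SOPs add nothing. If they already hold a step, what remains is to align Section 5.4 with them. No endpoint, sample size or analysis changes. The change is worth making because it is cheap and concerns safety.

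**What to change.** Keep confidentiality as the default in Section 5.4 and add a narrow exception that is disclosed at consent:

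- Have the PHQ-9 total checked before the participant leaves, for example as a score calculated in REDCap. This works whether the interviewer or the participant enters the answers.
- For a result above a threshold set by the clinical team, the interviewer gives referral information. With the participant's agreement, the interviewer also informs a designated clinician, who may be a member of the OAT clinic staff.
- Where the clinical team judges that there is an immediate safety risk, disclosure may go ahead despite the general bar.
- Replace the word anonymous with a statement that answers are confidential and linked by study ID. Section 5.4 already says that study instruments carry the participant number, so this only makes the wording consistent.
- Check that the consent form and SOPs say the same.

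The cost is a few sentences in Section 5, a short interviewer procedure using existing staff, and a small set-up task in REDCap. The downside is that a disclosed exception may make some participants slightly less candid on the depression items.
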